Effect of Flumazenil on Hypoactive Delirium in the ICU: A Double-Blind, Placebo-Controlled Pilot Study

NCT: 02899156

Document Date: September 25, 2017

Document Type: Study Protocol with Statistical Analysis

Objectives

The primary objectives was to determine the effect of flumazenil on delirium-free days for critically ill patients with benzodiazepine-associated hypoactive delirium. Delirium free days were defined as the number of days in the first 14 days during which the patient was alive without delirium or coma from any cause

The primary safety objective was the occurrence of severe refractory agitation, which was defined as RASS of +2 to +4 that did not resolve by decreasing the infusion rate of study drug.

Secondary outcomes included probability of delirium resolution, ICU LOS, maximum rate and duration of study infusion, rescue sedative use, and mechanical ventilator-free days.

The hypothesis was that flumazenil continuous infusion may decrease duration of delirium by reversing benzodiazepine-associated hypoactive delirium.

Study Design

This was a single-center randomized, double-blind, placebo-controlled study. Critically ill adult patients with suspected BZD-associated hypoactive delirium may be eligible.

Upon completion of screening and determining eligibility, patients received a test dose of flumazenil. If response was noted (defined as a change in RASS of +1 to +2), patients were randomized to receive standard of care and placebo infusion or standard of care and flumazenil infusion.

Methods

The PI or a co-investigator screened for subjects for inclusion via a daily drug utilization report of benzodiazepine use in the Intensive Care Units. Upon pre-qualification via EMR screening, the investigator performed an in-person assessment to confirm inclusion criteria have been met and patients do not meet exclusion criteria.

Screening included:

- review of the subjects current and prior to admission medication list (via medication reconciliation performed by PI/pharmacy medication reconciliation team, or urine drug toxicity screen)
- review of past medical history (history of seizure, TBI, etc.) to identify exclusion criteria

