- review of available urine drug toxicity screen to identify ingestion of pro-convulsant or home benzodiazepine medication. If there was no available urine drug toxicity screen and the patient was greater than 72 hrs from admission there was no requirement for ordering one unless there was a high suspicion for recreational drug use prior to admission
- review of available pregnancy test in females aged 18 -55 y.o. If pregnancy testing was not already performed, the PI discussed ordering a pregnancy test with the primary ICU attending prior to enrollment. If the pregnancy test was positive, the subject was not enrolled.

- all patients who were screened will be tabulated in order to document reasons for exclusion. PHI was not retained for this process.
- confirmed documentation of **RASS -3 to 0 and CAM-ICU positive**
- the study was then discussed with the primary attending physician caring for the patient and permission was obtained to approach patient and/or LAR to obtain consent. At that time the patient's home medication list was confirmed with the LAR to identify any history of taking pro-convulsants.

Test dose administration and monitoring (ICU-only):

- after consent was obtained enrollment into the trial occurred, subjects received a test dose of flumazenil 0.1-0.5 mg as IV push over 15 seconds administered by the bedside nurse. May repeat every 5-10 minutes up to a MAX of 2 mg total (assess for up to 60 minutes after last dose) (onset of 0.6 mg dose in healthy volunteers was 5 minutes).
- for all patients meeting inclusion criteria and for whom consent had been obtained the PI entered each subject's test dose response (positive/negative) on a study log
- subjects' response was assessed by the PI, bedside nurse and a member of the primary care team who remained at bedside for 30 minutes after the last test was administered
- a copy of the EKG was performed 10 minutes and 60 minutes after the first dose and was scanned into the subject's profile
- if response (defined as a change in RASS of +1 to +2) was noted, then randomization to standard of care and flumazenil or standard of care and placebo occurred
- responders had a sign posted on his/her door to indicate that the patient was part of a study
- patients that did not respond to test dose were not randomized

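### A woman aged 18-55 with no pregnancy test can be enrolled and given the open-label test dose, because the screening rule requires only a discussion about ordering a test and excludes only on a positive result

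*Combined protocol and SAP*

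**What the plan says.** The pregnancy check is one item in the screening list of the Methods section (Combined protocol and SAP). It has three parts:

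- What is looked at: "review of available pregnancy test in females aged 18 -55 y.o".
- What happens if no test exists: "If pregnancy testing was not already performed, the PI discussed ordering a pregnancy test with the primary ICU attending prior to enrollment".
- What blocks entry: "If the pregnancy test was positive, the subject was not enrolled".

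The section on test dose administration and monitoring then describes entry and first exposure: "after consent was obtained enrollment into the trial occurred, subjects received a test dose of flumazenil". This dose is open-label and comes before randomization, so every enrolled patient is meant to receive it, including those who do not respond and those later assigned to placebo.

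Two general statements also bear on the point. The Study Design section places the test dose after screening is finished and eligibility has been decided. The Methods section says that "the investigator performed an in-person assessment to confirm inclusion criteria have been met and patients do not meet exclusion criteria". The document refers to these criteria but does not set them out as a list.

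**The concern.** The bullet is evidently meant to keep pregnant women out of the trial. A test can leave the investigator in one of three states: positive, negative or no result. The bullet states a consequence for the first, implies one for the second, and for the third requires only a conversation with the ICU attending. A safety exclusion that acts only on a positive result cannot act on a patient who has no result.

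What is at stake is participant safety. A woman of unknown pregnancy status could receive flumazenil while the protocol was being followed to the letter. These patients have delirium, so their own history may be unreliable, and the history may have to come from the chart or the legally authorized representative. The point has no bearing on delirium-free days, the sample size or the analysis.

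**Working it through.** No arithmetic applies, and the plan gives no figure to reproduce. The check is to follow the written pathway from screening to the test dose and look for a step that requires a pregnancy result.

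**1. The branches of the pregnancy bullet (Methods, screening list)**

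| State of the test | What the document requires | Consequence for enrollment |
|---|---|---|
| Positive | Do not enroll | Barred |
| Negative | Nothing further | May proceed |
| None done, test ordered after the discussion | Discussion before enrollment | Not stated while the result is pending; screening is arguably incomplete |
| None done, no test ordered after the discussion | Discussion before enrollment | No bar stated |

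**2. The other steps before the test dose**

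- Review of medications and medical history: may reveal a known pregnancy, but requires no test.
- In-person assessment against the criteria: the same, and the criteria are not listed in this document.
- Review of the urine drug screen: unrelated to pregnancy.
- Confirmation of a RASS between -3 and 0 with a positive CAM-ICU: unrelated.
- Attending's permission and consent: no pregnancy result is named as a condition. The representative is asked to confirm home medications, with pro-convulsants as the stated purpose.
- Test dose: follows consent and enrollment, with no pregnancy condition in that step.

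The infusion, discontinuation and Statistical Analysis text does not mention pregnancy. No step therefore closes the fourth row of the table.

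**3. Comparison with the neighboring bullet**

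For a missing urine drug screen in a patient more than 72 hours from admission, the plan says plainly what is required: "there was no requirement for ordering one unless there was a high suspicion for recreational drug use prior to admission". So where the authors wanted to settle whether a missing test must be ordered, they did. The pregnancy bullet neither requires the order nor waives it.

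**4. Extent of exposure**

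The exposure that follows for every enrolled patient is the open-label test dose. The blinded infusion, in a phase of no more than 72 hours, reaches only test-dose responders who are randomized, and some of those receive placebo.

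**The case against.** The strongest reply is that the bullet, read as a whole, describes testing first. The discussion is tied to the time before enrollment, and the next sentence keeps a woman who tests positive from being enrolled. The drug-screen bullet contains an express waiver and the pregnancy bullet does not, which suggests that a test was expected. The Study Design section also gives the test dose only once screening is complete and eligibility decided. If a test has been ordered and is pending, screening is arguably not complete. That argument stands and largely answers the pending-result case. It does not answer the case where no test is ordered: the discussion has taken place, the item can be counted as done, and the text states no consequence.

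A second reply is that a separate list of exclusion criteria may exist. It may, and the finding is limited to what this document contains. But an entry that merely excludes pregnant patients would not bar an untested woman whose status is unknown. Only an entry that requires a negative result would, and then this bullet would be looser than the list.

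A third reply is that a discussion leaves room for judgment, for example about a woman who has had a hysterectomy. That is a fair point about the remedy, and a blanket rule for every woman aged 18 to 55 would be too blunt.

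A reader might also infer more than the text supports:

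- That the exclusion has no chance of working without a test. It does not follow, because history review, the in-person assessment or the representative could bring a known pregnancy to light. Only the test-based part of the exclusion fails.
- That every affected woman faces up to 72 hours of infused flumazenil. That applies only to randomized responders in the active arm.
- That untested women were in fact dosed. Nothing in the document shows this.

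**Conclusion.** The point holds in a narrow form. For a woman aged 18 to 55 with no pregnancy test, the document requires a discussion about ordering one, and only a positive result bars her. If no test is ordered, nothing in the document stops enrollment and the open-label test dose. This is a safety rule that falls short of its own purpose, and more than a missing detail, because the document does prescribe an action for the untested case and that action does not produce a result.

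The size cannot be stated. The document does not say how many screened women were in the age range or how many had no test, so neither a number nor a defensible range can be given. The conclusion assumes that no separate exclusion list requires a negative result and that the bullet is applied as worded. It should be corrected for participant safety; it does not change any statistical result.

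**What to change.** Amend the pregnancy item in the screening list so that a woman aged 18 to 55 who could be pregnant is not enrolled until a negative pregnancy result is available, before the test dose. The sponsor should settle two details that the plan leaves open: how recent the test must be, and how to document that a woman in this age range cannot be pregnant, so that she is not excluded needlessly. If a separate exclusion list exists, the two texts should be reconciled.

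The cost is one or two sentences, plus a routine test or a short delay for a few candidates, or the loss of those for whom no result is obtained. This adds an explicit entry condition to the plan, but one that serves the exclusion it already states. No dose, endpoint or analysis changes.

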- to ensure proper safety monitoring, the PI, a member of the primary care, and the bedside nurse (administering) were present to monitor for any complications for 30 minutes after the last test dose.

Infusion titration post-randomization (ICU-only):

1. Responders to flumazenil:
 - standard of care + flumazenil 2.5 mg/50 mLs 0.9% NaCl, or 5% dextrose (0.05 mg/mL) IV continuous infusion
 - Dosing range: 0.025 mg/hr – 0.3 mg/hr (0.5 -6 ml/hr)
 - Start at @ 2 mLs per hour (0.1 mg/hr., 2.4 mg/24 hours)
 - Titration by 1 mL (0.05 mg) or as clinically indicated per study investigator every 60 minutes for target RASS (0 to +1)
**Patient care order placed for nurse to monitor RASS every 1 hour (standard of care is every 2 hrs.).
 - Maximum Rate: 6 mLs/hr. (0.3 mg/hr.)
 - If RASS +2 to +3, decrease dose by 0.05mg (1 mL) or as clinically indicated per study investigator every 60 minutes or HOLD if at the lowest rate of 0.025 mg/hr (0.5ml/hr) and re-assess in 1 hour.
 - If RASS +4, HOLD regardless of rate and re-assess in 1 hour.
 - standard of care + placebo (50 mLs 0.9% NaCl, 5% dextrose) IV continuous infusion

- Dosing range: 0.025 mg/hr – 0.3 mg/hr (0.5 -6 ml/hr)
 - Start at @ 2 mLs per hour
 - Titration by 1 mL (0.05 mg) or as clinically indicated per study investigator every 60 minutes for target RASS (0 to +1)
 - Maximum Rate: 6mLs/hr. (0.3 mg/hr.)
 - If RASS +2 to +3, decrease dose by 0.05mg (1 mL) or as clinically indicated per study investigator every 60 minutes or HOLD if at the lowest rate of 0.025 mg/hr (0.5ml/hr) and re-assess in 1 hour.
 - If RASS +4, HOLD regardless of rate and re-assess in 1 hour.
2. PI or co-investigator assessed patient response daily during the intervention phase (no longer than 72 hours).
- Daily interruption of infusion starting @ 0900 for 4 hours or until RASS of -1 to -2 .
 - A. Assess & document CAM-ICU and RASS BEFORE continuous infusion is interrupted
 - B. At the end of the interruption, assess patient’s RASS and CAM-ICU.
 - C. If patient regresses back to RASS -1 to -3 and CAM-ICU positive, then study infusion was restarted at the previous rate and re-assessed daily.
 - D. If daily interruption results in no change in RASS or CAM-ICU scores then study infusion was restarted @ the previous rate
 - Daily interruption occurred daily unless one of the following criteria were met resulting in discontinuation of study drug in the interim:
 - A. Primary attending caring for patient deemed discontinuation appropriate

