 - a. Primary care team must *prospectively* notify the PI if the primary care team wishes to interrupt or discontinue the study infusion to provide clinical care to the patient.
 - B. RASS +2 to +4 while on infusion and agitation not controlled with standard treatments (i.e. anti-psychotics)
 - C. Rescue benzodiazepine needed due to signs of withdrawal according to the SHOT Scale
 - D. Remains CAM-ICU negative after interruption
 - E. ICU discharge (determined by physical transfer to lower level of care)
 - F. Adverse event attributable to study drug (i.e. supraventricular arrhythmia, seizure)
3. If episodic sedation was needed for a procedure (i.e. bronchoscopy)
- Study drug could be held (i.e. 30-60 minutes prior) and once the procedure was completed the study infusion could be restarted at previous rate.

As delineated above, the primary investigator and co-investigators were active participants in the study from pre-screening, enrollment, data collection, and data analysis. Relevant staff, including nursing personnel and medical staff, were utilized for coordination purposes.

Statistical Analysis

Baseline characteristics included age, sex, ICU service, Sequential Organ Failure Assessment (SOFA) score, Charlson Comorbidity Index, days in hospital prior to enrollment, time since last benzodiazepine administration, benzodiazepine indication, lorazepam equivalents (lorazepam 1 mg = midazolam 2 mg = diazepam 5 mg), home benzodiazepine use, and RASS prior to test dose. The original sample size calculation indicated that 40 patients in each group were required to detect a 30% difference (sd \pm 2 d) in delirium-free days, assuming p value less than 0.05 and 80% power. Descriptive statistics and the Wilcoxon rank-sum test were performed. The Kaplan–Meier method was used to characterize the probability of being delirium and coma free.

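### Both test-dose EKGs are timed from the first dose, so with small increments part of the test dose can follow the last scheduled EKG

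*Combined protocol and SAP*

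**What the plan says.** All of this stands under *Test dose administration and monitoring (ICU-only)* unless noted.

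- **Dose:** "subjects received a test dose of flumazenil 0.1-0.5 mg as IV push over 15 seconds".
- **Repeats:** "May repeat every 5-10 minutes up to a MAX of 2 mg total".
- **EKGs:** "EKG was performed 10 minutes and 60 minutes after the first dose". The document schedules no other EKG, either here or during the infusion.
- **Response assessment:** "assess for up to 60 minutes after last dose".
- **Bedside presence:** the investigator, the nurse and a member of the primary team stay "for 30 minutes after the last test dose".

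The infusion section lists reasons for stopping study drug. Criterion F there is an adverse event attributed to the drug, with supraventricular arrhythmia and seizure as its examples.

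The plan sets no limit on the length of the test-dose phase. It does not say what happens to the EKG times if dosing continues past 60 minutes. It defines a response by RASS, but writes no rule that repeats stop once a response is seen.

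**The concern.** The EKGs run on a different clock from the rest of the test-dose monitoring. Two of the three monitoring activities follow the last dose, so they adapt to however many boluses are given. The EKGs stay fixed to the first dose and do not adapt.

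Three features make this worth checking:

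- Every enrolled patient receives the active test dose, including those later assigned to placebo and those never randomized.
- The patients most likely to approach 2 mg are those who respond late or not at all. Non-responders are not randomized, and the document describes no later study monitoring for them.
- The position of the second EKG relative to cumulative dose depends on the increment and interval chosen at the bedside. EKG findings from different patients would then reflect different exposures.

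If dosing passes 60 minutes, a patient with the highest test-dose exposure has no planned EKG after the complete dose, and a responder could go on to randomization without one.

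**Working it through.** The plan gives no duration for the test-dose phase, so there is no stated figure to reproduce. The check is schedule arithmetic.

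**Inputs (all from the test-dose section):** step size d = 0.1 to 0.5 mg; interval t = 5 to 10 minutes; ceiling 2 mg; EKGs at 10 and 60 minutes from the first dose.

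**Assumptions:** constant step size and interval, and the full 2 mg given.

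**Step 1: time of the last dose.** Number of doses n = 2/d, rounded up. Last dose at (n − 1) × t.

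| Step | Doses to 2 mg | Last dose, every 5 min | Last dose, every 10 min |
|---|---|---|---|
| 0.1 mg | 20 | 19 × 5 = 95 min | 19 × 10 = 190 min |
| 0.2 mg | 10 | 9 × 5 = 45 min | 9 × 10 = 90 min |
| 0.25 mg | 8 | 7 × 5 = 35 min | 7 × 10 = 70 min |
| 0.3 mg | 7 (the last is 0.2 mg) | 6 × 5 = 30 min | 6 × 10 = 60 min |
| 0.5 mg | 4 | 3 × 5 = 15 min | 3 × 10 = 30 min |

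Dosing always passes 60 minutes at 0.1 mg, and can pass it at 0.2 and 0.25 mg. It does not pass it at 0.3 mg or more.

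**Step 2: amount given by the 60-minute EKG.** A dose due exactly at 60 minutes is counted both ways, which gives the ranges.

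| Schedule | Doses by 60 min | Given | Still to come |
|---|---|---|---|
| 0.1 mg every 5 min | 12–13 | 1.2–1.3 mg | 0.7–0.8 mg (35–40%) |
| 0.1 mg every 10 min | 6–7 | 0.6–0.7 mg | 1.3–1.4 mg (65–70%) |
| 0.2 mg every 5 min | 10 | 2.0 mg | 0 |
| 0.2 mg every 10 min | 6–7 | 1.2–1.4 mg | 0.6–0.8 mg (30–40%) |
| 0.5 mg, any interval | 4 | 2.0 mg | 0 |

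In the slowest case the last dose comes 190 − 60 = 130 minutes after the second EKG. At 0.5 mg the second EKG comes 30 to 45 minutes after the last dose.

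**Step 3: the 10-minute EKG.** On the fastest schedule (0.5 mg every 5 minutes), doses fall at 0, 5 and 10 minutes, so at most 1.5 mg has been given. This EKG can never follow a full 2 mg, so only the later one could.

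**Step 4: when more than half of the 2 mg follows both EKGs.** With 0.1 mg steps, at most 9 doses may fall by 60 minutes, which needs an interval above 60/9, or about 6.7 minutes. At 10-minute intervals, counting the dose due at 60 minutes as before the EKG, 7 × d must be below 1 mg, so d is at most about 0.14 mg (7 × 0.14 = 0.98 mg).

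**The case against.** **The two anchors do not contradict each other.** EKGs and bedside assessment are different measurements, and each can be carried out as written. This stands: the plan can be followed. What it lacks is any provision for the EKGs when its own schedule runs past 60 minutes.

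**The long schedules may be rare.** The 2 mg is a maximum, and a patient who responds early may receive less. The document gives no frequency for any increment. This also stands, and it limits the claim to what the plan permits. A reader might infer that both EKGs usually precede most of the test dose. The documents do not support that: Step 4 shows that it needs steps near the 0.1 mg minimum, longer intervals and the full 2 mg.

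**Late doses are observed.** A reader might infer that an arrhythmia after a late dose would escape planned monitoring. That goes too far, because the bedside presence is described as safety monitoring and is counted from the last dose. The plan also never states what the EKGs are for. Their safety purpose is inferred from their place in the monitoring section, and criterion F concerns the infusion after randomization, not the test dose.

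**No planned result depends on it.** The primary safety objective is severe refractory agitation, no EKG endpoint is analysed, and the test dose precedes randomization. This stands: the randomized comparison is not affected.

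**Moving both EKGs would have a cost.** Anchored to the last dose under 0.1 mg every 10 minutes, they would fall at 190 + 10 = 200 and 190 + 60 = 250 minutes after first exposure, and the early check would be lost. This stands and narrows the remedy to the later EKG.

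**Conclusion.** The concern holds in a limited form. Under permitted schedules with small increments, part of the test dose can follow the last scheduled EKG: 35 to 70% of 2 mg with 0.1 mg steps, and 30 to 40% with 0.2 mg every 10 minutes. It does not arise at 0.3 mg or above, nor at 0.2 mg every 5 minutes.

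The sizes rest on equal steps, a constant interval and the full 2 mg, none of which the plan requires and all of which it allows. That the EKGs serve safety is an inference.

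This is a gap in EKG coverage of the test dose, not an absence of monitoring and not a threat to the efficacy comparison. It is still more than a missing detail, because these are the only EKGs scheduled and the mismatch follows from the plan's own figures.

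**What to change.** Reconcile the time anchor of the later planned EKG with the repeat-dose schedule and with the last-dose anchor used for response assessment and bedside presence. The aim is that at least one of the two planned EKGs follows the complete test dose under every permitted increment and interval, while the early EKG is kept. The investigators should decide the timing.

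The cost is about one line of protocol wording and no additional EKG. The downside is that the clock time of the later EKG will vary with the number of doses given.

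### Cheap precision gain: adjust the delirium-free-days comparison for baseline data already collected, report the difference in days with an interval, and restate the sizing in days

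*Combined protocol and SAP*

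**What the plan says.** Everything that bears on this is in the Statistical Analysis section of the combined protocol and SAP, with eligibility under Methods.

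- **Test.** "Descriptive statistics and the Wilcoxon rank-sum test were performed". The section does not tie the test to an outcome; I take it to be the test for delirium-free days, the primary outcome, a count from 0 to 14. Kaplan–Meier is descriptive only: the "method was used to characterize the probability of being delirium and coma free". No regression model, stratification or adjusted analysis is named, and no difference in days with a confidence interval.
- **Baseline data.** "Baseline characteristics included age, sex, ICU service, Sequential Organ Failure Assessment (SOFA) score, Charlson Comorbidity Index", followed by others that include "lorazepam equivalents (lorazepam 1 mg = midazolam 2 mg = diazepam 5 mg") and "home benzodiazepine use, and RASS prior to test dose". None is said to enter the comparison.
- **Sizing.** "The original sample size calculation indicated that 40 patients in each group were required to detect a 30% difference" in delirium-free days, with SD 2 days, p below 0.05 and 80% power. There is no control mean, no difference in days and no sidedness, and the section does not say whether the 30% is relative.
- **Who is randomized.** Entry requires "RASS -3 to 0 and CAM-ICU positive", and "patients that did not respond to test dose were not randomized".

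**The concern.** In critically ill patients, severity of illness, benzodiazepine exposure and depth of sedation at entry could plausibly predict days alive without delirium or coma. If they do, a comparison that ignores them leaves that variation in the error term and gives away precision that needs no extra patient, visit or measurement. If they do not, adjustment costs a little. The question is where the balance lies at this sample size.

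A related gap is that the trial was sized on a difference in days, but no estimate of that difference with an interval is named. Descriptive statistics may show days by arm. They would not show how precisely the difference is known, or whether the data exclude the difference used for planning.

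**Working it through.** **1. The plan's sizing.** The 40 per group cannot be computed forward because the control mean is missing, so I invert it. For a two-sample t-test with n = 40 per group, two-sided 0.05 and 80% power, the standardized difference is 0.634.

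- Difference: 0.634 × 2 = 1.27 days.
- If the 30% is relative, the control mean is 1.27 / 0.30 = 4.23 days.
- One-sided, the standardized difference is 0.561, and 0.561 × 2 / 0.30 = 3.74 days.

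The answer depends heavily on the missing mean. At SD 2 and a relative 30%, control means of 3, 4 and 5 days give power of 51, 75 and 91% with 40 per group, and need 79, 45 and 29 per group for 80%.

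**2. Break-even for adjustment.** With k covariates and N patients, the expected ratio of adjusted to unadjusted variance of the difference in means is (1 − R²)(N − 3)/(N − 3 − k). It equals 1 at R² = k/(N − 3). With k = 3:

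- N = 80: 3/77 = 0.039
- N = 40: 3/37 = 0.081
- N = 20: 3/17 = 0.176

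At N = 80 and R² = 0 the ratio is 77/74 = 1.041, the price of adjusting for nothing.

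**3. Power of the two tests.** Simulation with 20,000 trials per setting (95% Monte Carlo error about 0.7 points). Control mean is 4.23, difference 1.27, SD 2; days are rounded and kept within 0 to 14. Three independent covariates share R² equally, with RASS cut to four levels. The tie-corrected rank-sum test is compared with a linear model on ranked days, arm and ranked covariates. All R² values are assumptions.

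| R² (total) | Rank-sum, 40 per group | Rank ANCOVA, 40 per group | Rank-sum sample size with the same power |
|---|---|---|---|
| 0 | 77.1% | 75.9% | 38 |
| 0.05 | 77.4% | 77.7% | 40 |
| 0.10 | 77.5% | 79.7% | 42 |
| 0.20 | 77.0% | 83.1% | 46 |
| 0.30 | 77.1% | 87.2% | 52 |

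Type I error of rank ANCOVA was 4.8 to 5.3% at 40, 20 and 10 per arm. On scores heaped at both ends (10% of controls at 0 and 10% at 11), the pattern held: 77.1 to 75.6%, 77.0 to 82.8% and 77.5 to 87.6% at R² 0, 0.2 and 0.3.

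**4. Larger SD and smaller trials, three covariates.**

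- SD 3, 40 per group: about 44% becomes 43, 46, 50 and 55% at R² 0, 0.1, 0.2 and 0.3.
- SD 2, 20 per arm: about 47% becomes 44, 48, 52 and 56%.
- SD 2, 10 per arm: about 25% becomes 23, 24, 26 and 28%.

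**5. Fewer covariates in a smaller trial.** With two covariates at 20 per arm, power goes from 47.2 to 45.7% at total R² 0, from 46.9 to 49.7% at 0.2 and from 46.4 to 52.5% at 0.3. With one covariate at 10 per arm, it goes from 25.2 to 25.1%, 24.4 to 25.4% and 25.3 to 27.1%. The loss at R² 0 shrinks, and so does the gain at 0.2 and 0.3.

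**6. Interval width.** Unadjusted, 40 per group: 1.99 × 2 × √(2/40) = 0.89 days half-width. Adjusted, in simulation: 0.91, 0.87, 0.82 and 0.77 days at R² 0, 0.1, 0.2 and 0.3. Coverage of the model-based interval was 94.6 to 95.3%.

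**7. Sizing for the test used.** At 1.27 days the rank-sum test has about 77% power. Rescaling, 1.27 × (1.96 + 0.84)/(1.96 + 0.74) = 1.32, so it reaches 80% at about 1.3 days.

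**The case against.** **It is a refinement, not an error.** The title calls this a pilot, and an unadjusted rank-sum test is valid and conventional. This stands. A reader might infer that the primary test is biased or wrong; nothing in the documents supports that.

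**The gain is hypothetical.** The documents give no R². RASS is confined to four levels at entry and only test-dose responders are randomized, so prediction may be weak. At R² 0.05 the gain is 0.3 points, inside simulation error. This stands, and the benefit is stated only as conditional.

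**It may be too late or the trial too small.** The section is in the past tense and calls its sample size calculation the original one; it does not give the number randomized. If arm-level data have been seen, the gain cannot properly reach the primary test. If about 20 were randomized, there is no material gain. Both stand as conditions, because the documents settle neither.

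**A covariate cap might seem to rescue small trials.** A reader could compute break-evens of 2/37 = 0.054 for two covariates at 40 patients and 1/17 = 0.059 for one at 20, and infer that the cap keeps the threshold low. Those figures count only the variance explained by the covariates kept. If the three share R² equally, the total needed is 0.054 × 3/2 = 0.081 and 0.059 × 3 = 0.176, the same as with all three. The cap limits the loss; it does not lower the break-even on total R².

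**Rank ANCOVA is one choice among several.** An adjusted proportional-odds model would also serve. Rank ANCOVA is suggested because it stays closest to the test named.

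**Conclusion.** The point holds as a low-cost improvement in precision. At the planned 40 per group, adjusting for the three covariates risks about one power point and gains about 2, 6 or 10 points if they explain 10, 20 or 30% of the variance. The last two are worth about 46 or 52 per group instead of 40. This rests on assumed R² values, SD 2, a difference of 1.27 days and 80 patients randomized. At 40 patients in total the break-even doubles to 8%; at 20 it is 18%.

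The sizing point needs no R² assumption. As written, 40 per group cannot be verified. A reader might go further and infer that 40 is wrong or that the trial was underpowered. The documents do not support that: 40 is right for a two-sided t-test if the 30% is relative and the control mean is about 4.2 days. What is missing are the inputs that would show it, and a statement for the rank test, for which power at 1.27 days is about 77%.

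**What to change.** **If arm-level data have not been seen**, specify in the Statistical Analysis section:

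- Primary analysis of delirium-free days by rank ANCOVA: ranked days on arm and ranked baseline covariates, two-sided 0.05.
- Covariates and their order fixed beforehand: SOFA, lorazepam equivalents, pre-test-dose RASS, with fewer if far fewer than 80 are randomized. The order is a suggestion, with RASS last because eligibility restricts it. A missing baseline value takes the pooled median, so every randomized patient is kept.
- The unadjusted rank-sum test as sensitivity analysis.
- The adjusted difference in days with a model-based 95% CI from a linear model on the same covariates, for estimation only, with no second p value.

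**If arm-level data have been seen**, keep the rank-sum test as primary and label both the adjusted analysis and the difference in days supplementary.

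**Sizing, in either case.** State the control mean, whether the 30% is relative, the sidedness and the source of the SD. Give the difference in days for the test used. At 40 per group, SD 2 and two-sided 0.05, 1.27 days has 80% power by t-test, about 77% by rank-sum, and about 76% by rank ANCOVA if the covariates carry no information. Add the figure for the number actually randomized; by t-test at SD 2, the difference detectable with 80% power is 1.82 days at 20 per group and 2.65 at 10.

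**Cost.** SAP wording and two short models on data already held. If the covariates carry no information, power at 40 per group falls from 77.1 to 75.9% and the CI half-width rises from 0.89 to 0.91 days.
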